7.2 Secondary Endpoints

For the secondary endpoint, we will use descriptive data on signal to background noise and safety data by tumor type to identify optimal dosing and timing of indocyanine green for intraoperative imaging in nervous system tumors. We will conduct an interim analysis after approximately 185 subjects are treated at the 2.5mg dose and 185 at the 5mg/kg dose.

Other important endpoints include safety and toxicity that includes review of vital signs and any reported or observed AE.

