VATS – Video Assisted Thoracoscopic Surgeries

CONFIDENTIAL

This material is the property of the University of Pennsylvania.

Study Summary

Title	Two-Part Study to Evaluate the Safety and Efficacy of Image Guided Surgery using Near-Infrared Dyes for Intramolecular Imaging of Nervous System Tumors Compared to Standard of Care, (TumorGlow™)
Short Title	Indocyanine Green for All Nervous System Tumors
Protocol/IRB Number	822231/UPCC #09315
Phase	Phase I/II
Methodology	Open Label; Part 1 observational and Part 2 permitting deviation from surgical plan based on indocyanine green intraoperative imaging.
Study Duration	5 years
Clinical Sites	Penn Medicine: Hospital of the University of Pennsylvania Penn Medicine Pennsylvania Hospital Penn Medicine Presbyterian Hospital
Objectives	
Part I: To determine safety/efficacy of high dose, delayed indocyanine green (second window ICG) during surgery of nervous system tumors.
 
Part II: To determine diagnostic test characteristics (sensitivity/specificity) of delayed, high dose indocyanine green (second window ICG) as a diagnostic aid during surgery of nervous system tumors.
 
Part IIb: To optimize timing and dose of second window IcG during surgery of nervous system tumors, based on sensitivity/specificity.
 
Part IIc: Compare SOC dyes with indocyanine green to determine efficacy for tumor visualization, answering the question is one dye superior to another, more accurate and precise.

Number of Subjects	We intend on enrolling 500 subjects in this study.
Diagnosis and Main Inclusion Criteria	Patients presenting with suspected resectable nervous system tumors who are considered to be good surgical candidates and are at risk of local recurrence.
Investigational Product, Dose, Route, Regimen	The study drug is indocyanine green, single dose of up to 5 mg/kg administered up to 72 hours prior to resection or a single dose of 25 mg administered during induction, diluted into sterile water for intravenous (IV) injection prior to tumor resection. Dye and dose plan is determined by PI based on tumor type, surgical timing, and signal to background ratio.

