1.6 Dose Rationale

In this study, the indocyanine green dose began at 5 mg/kg, aligned with previous nonclinical and clinical experience at the University of Pennsylvania. Given the incidence of HTN in our CNS cohort and seeking optimal signal to background ratio, we decreased to 2.5 mg/kg to assess efficacy and safety. Thus, we intend to evaluate dose ranges but will not exceed 5mg/kg. Alternately, based on neurosurgeon plan, patients may receive a 25 mg bolus of ICG at the time of induction administered intravenously by the anesthesiologist. This 25 mg dose of indocyanine green is similar to dosing for other intraoperative vascular visualization. This can cause less usage of the drug, lower risk of adverse event occurrences.

We make no changes to the route of administration.. The most important difference between what is labeled on the package and this protocol is the dose regimen (up to 5 mg/kg) and the amount of time elapsing before intraoperative imaging begins (up to 72 hours). This protocol began with 24-hour infusions the day before surgery based on previous nonclinical and clinical experience at the University of Pennsylvania. Interested in strength of signal to background ratio over extended or shortened timeframes, we allow for a range of up to 72 hours. The rationale for dosing timing prior to surgical intervention is based on the minimal risks with indocyanine exposure, to accommodate logistical scheduling of surgeries, and to collect data on optimal signal to background ratio in various tumor types.

Indocyanine green has been used in a dose-escalation trial up to a maximum dose of 10 mg/kg [\[22\]](#) and in other trials 3-5 mg/kg [\[13, 17-21\]](#). Indocyanine green has a LD₅₀ after IV administration of 50 to 75 mg/kg [\[22\]](#).

As [name] and other researchers have used an IV injection of indocyanine green to obtain imaging sufficient to describe discrepancies in the structure of abnormal hyper-vascularized tissue [\[47\]](#), it therefore stands to reason that we would be able to accomplish our objective of imaging tumors with indocyanine green using a similar dose.

CONFIDENTIAL

This material is the property of the University of Pennsylvania.

Interim data analysis (see [Section 7.2](#)), specifically the fluorescence signal to background ratio, will determine the optimal timing of indocyanine green infusion, which will guide future infusion in this protocol and future protocols.

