1.7.3 Assessment of Potential Risks and Benefits

The PI weighs the risks of participating in the study with the potential benefits of participating in the study for each subject enrolled. We feel that the very low risk of adverse reactions expected from the study compared to the practical potential benefit of improving nervous system tumor resection and related outcomes using a non-toxic imaging agent are acceptable.

2 Study Objectives

The primary study objective is to determine safety/efficacy of high dose, delayed indocyanine green (second window ICG) during surgery of nervous system tumors.

The first objective is to determine diagnostic test characteristics (sensitivity/specificity) of delayed, high dose indocyanine green (second window ICG) as a diagnostic aid during surgery of nervous system tumors. Additionally, to optimize timing and dose of second window IcG during surgery of nervous system tumors, based on sensitivity/specificity. Lastly, to compare SOC dyes with indocyanine green to determine efficacy for tumor visualization, answering the question is one dye superior to another, more accurate and precise.

3 Study Design

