3.3 Secondary Study Endpoints

The secondary end-point of the study is to identify based on signal to background noise the optimal timing for surgery following infusion of indocyanine green and dose for optimal safety without toxicity for visualization of indocyanine green during intraoperative imaging in nervous system tumors.

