7.1 Primary Endpoint

The primary endpoint is the sensitivity, specificity, positive predictive value, negative predictive value of indocyanine green fluorescence as compared to the gold standard – H&E histopathology.

We compute estimates of the sensitivity (fraction of path-positive margins that are called correctly) and specificity (fraction of path-negative margins that are called correctly), and calculate Bayesian 90% probability intervals around them. We estimate the sensitivity of our method by evaluating the fraction of marginal biopsy and/or resected specimens that we call correctly, and similarly estimate the specificity by the fraction of path-negative biopsy and/or resected specimens that we call correctly.

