7.4 Statistical Methods

All data are summarized, with means and standard deviations for continuous variables and proportions for categorical variables. Graphical techniques will be used for data exploration. Analyses will be primarily descriptive. The remainder of the statistical approaches is described above.

8 Safety and Adverse Events

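### Part IIb is to optimise dose and timing on sensitivity and specificity, but its endpoint and analysis use signal to background and safety, and no accuracy by dose or interval is planned

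*Combined protocol and SAP*

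**What the plan says.** The objective appears twice. The Study Summary has "Part IIb: To optimize timing and dose of second window IcG during surgery of nervous system tumors, based on sensitivity/specificity", and section 2 (Study Objectives) repeats it: "to optimize timing and dose of second window IcG during surgery of nervous system tumors, based on sensitivity/specificity".

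The passages that put the objective into practice use a different measure:

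- Section 3.3 defines the secondary endpoint: "identify based on signal to background noise the optimal timing for surgery following infusion of indocyanine green and dose for optimal safety without toxicity".
- Section 7.2 gives the analysis: "we will use descriptive data on signal to background noise and safety data by tumor type to identify optimal dosing and timing". It places an interim analysis after about 185 subjects at each of two doses.
- Section 1.6 says of that interim analysis: "specifically the fluorescence signal to background ratio, will determine the optimal timing of indocyanine green infusion, which will guide future infusion in this protocol". It extends this to future protocols.
- The product row of the Study Summary lists signal to background, with tumor type and surgical timing, as the basis on which the PI sets the dye and dose plan.

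Sensitivity and specificity are analysed only in section 7.1, against H&E histopathology, with 90% Bayesian intervals and no breakdown by dose or time since infusion. Section 7.4 closes the plan: "Analyses will be primarily descriptive. The remainder of the statistical approaches is described above".

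**The concern.** Signal to background measures contrast. Sensitivity and specificity measure agreement with histology at the specimen level. The documents give no rule that converts one into the other, so a conclusion on the first does not answer an objective stated in terms of the second.

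A regimen could therefore be declared optimal under Part IIb while its agreement with histology, the criterion the objective names, was never tabulated for that regimen. That conclusion would then be used. Section 1.6 lets the interim result steer later infusions here and in other protocols, and section 7.3 says the study is meant to inform a future randomised trial. Section 1.6 also says of the dose change "we decreased to 2.5 mg/kg to assess efficacy and safety", but no planned accuracy analysis separates the two doses.

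**Working it through.** **Step 1: passages side by side.** The plan states no figure for Part IIb that could be reproduced, so the main check is textual.

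| Place | Criterion for dose or timing |
|---|---|
| Study Summary, Part IIb objective | sensitivity/specificity |
| Section 2 | sensitivity/specificity |
| Study Summary, product row | tumor type, surgical timing, signal to background |
| Section 1.6, interim | signal to background (timing) |
| Section 3.3 | signal to background, safety |
| Section 7.2 | signal to background and safety, by tumor type |
| Section 7.1 | accuracy estimated, but not by dose or interval |
| Section 7.4 | refers back; adds nothing on dose or timing |

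Two places name accuracy, four name signal to background, and none plans accuracy by regimen.

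**Step 2: how many subjects the interim could still guide.** Inputs are 186 subjects infused at 5 mg/kg and 110 at 2.5 mg/kg by January 2019, out of 327 consented and 296 infused (section 1.5); about 185 per dose at the interim (section 7.2); and 500 planned (section 7.3). Section 7.2 writes the lower dose as 2.5mg where sections 1.5 and 1.6 write 2.5 mg/kg. It is read here as 2.5 mg/kg, and the passages should be reconciled.

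- Still to be infused at 2.5 mg/kg before the interim: 185 − 110 = 75. On these counts the interim had not been reached in January 2019.
- Infused by the interim: 186 + 185 = 371.
- If 500 counts infused subjects: 500 − 371 = 129 remain, and 129/500 = 26%.
- If 500 counts consented subjects, and the infusion rate to date continues (an assumption): 500 × 296/327 ≈ 453 infused, 453 − 371 = 82 remain, and 82/500 = 16%.

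The range is therefore roughly 80 to 130. These are not strict bounds, because section 7.2 says approximately 185. Further 5 mg/kg subjects, or any given 25 mg at induction, before the interim would lower them.

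**Step 3: what a table by regimen could show (illustrative only).** The documents give no specimen counts. Assume one independent specimen per subject, 185 per dose, a path-positive share of 50%, 70% or 90%, a specificity of 80% and a uniform prior. The 90% interval comes from Beta(x + 1, n − x + 1), where x is the number called correctly out of n path-negative specimens.

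| Path-positive share | Path-negative per dose | Half-width | Path-negative per cell, 3 interval bands | Half-width |
|---|---|---|---|---|
| 50% | 92 | 7 points | 31 | 12 points |
| 70% | 55 | 9 points | 18 | 16 points |
| 90% | 18 | 16 points | 6 | 23 points |

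Clustering of specimens within patients, or a split by tumor type, would widen these. They describe the table that is absent. They do not measure the size of the inconsistency.

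**The case against.** The strongest reply is that signal to background is the real criterion and the accuracy phrase is a stray one. The phrase occurs in one objective stated twice, while four places use signal to background. The plan also calls itself primarily descriptive, has no sample size calculation and claims no formal dose comparison. Much of this stands. It makes rewording the objective a legitimate answer, and it limits the harm. It does not remove the conflict, because an objective that appears in both the summary and the body is what a report would be held to.

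A reader might be tempted further, in four ways that the documents do not support:

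- That accuracy was the true intent and its analysis was lost. The text does not settle which criterion was meant.
- That accuracy by dose will never be examined, or that section 7.1 forbids it. Section 7.1 is silent on stratification. The finding is only that no such analysis is planned.
- That the interim signal-to-background result chooses the dose. Section 1.6 ties it to timing; dose enters through sections 3.3 and 7.2.
- That signal to background would pick a less accurate regimen, or that accuracy by dose would be too imprecise to use. No data given bear on the first, and the second depends wholly on assumed specimen counts.

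**Conclusion.** The point holds as an inconsistency between objective and analysis. Part IIb is defined on sensitivity and specificity, its endpoint and analysis are defined on signal to background and safety, and nothing in sections 7.1 to 7.4 connects the two. This rests on the text alone and needs no assumption.

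The practical reach within this study is the roughly 80 to 130 subjects whose infusion the interim could still guide, given the reading of the 2.5mg figure and the infusion rate assumed above. Beyond that, the effect is on later protocols. The primary endpoint is untouched. The correction should be made, but the point does not undermine the study as a whole. Any comparison of regimens will be exploratory whichever criterion is kept, since the neurosurgeon chooses dose and time (section 3.1) and there is no randomisation (section 5.3). Nothing here favours one dose or timing over another.

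**What to change.** Reconcile the Study Summary (Part IIb objective and product row) with sections 1.6, 2, 3.3 and 7.2, by one of two routes.

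**(a) Keep the accuracy criterion.** Add to section 7.2 a descriptive table of specimen-level sensitivity and specificity, shown with signal to background and safety:

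- by dose group and by infusion-to-imaging interval bands fixed before the interim;
- by tumor type, or adjusted for it where cells are small, because the Study Summary ties the dose plan to tumor type and section 7.2 already describes results that way;
- with 90% intervals that allow for several specimens per patient;
- with subjects given 25 mg at induction shown separately, since theirs is not the delayed, high-dose regimen that Part IIb concerns;
- labelled exploratory.

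**(b) Keep signal to background and safety.** Reword the Part IIb objective in both places to say so, and make no claim of optimisation on accuracy.

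**Cost.** Either route is a protocol amendment, which section 11 sends to the IRB. Route (a) adds one descriptive table from specimens already analysed for the primary endpoint, with no extra patients or tests. Its drawback is wide intervals in small cells. It also requires that infusion-to-imaging time is captured; this must be confirmed, because the case report forms are an attachment not available here. Route (b) adds no analysis, but gives up the accuracy claim for Part IIb.

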7.3 Sample Size Determination

There is no sample size calculation for this study as the purpose here is to assess safety and feasibility of using indocyanine green as an imaging agent for viewing

CONFIDENTIAL

This material is the property of the University of Pennsylvania.

with NIR imaging systems during nervous system tumor surgery. To accomplish this goal, we propose a 500 patient non-randomized prospective design with annual follow-up for 5 years. This is intended to inform the design and planning of a future randomized study.

7.4 Statistical Methods

All data are summarized, with means and standard deviations for continuous variables and proportions for categorical variables. Graphical techniques will be used for data exploration. Analyses will be primarily descriptive. The remainder of the statistical approaches is described above.

8 Safety and Adverse Events

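### Optimal dose and timing are to be identified by tumour type from means, SDs and proportions, with no interval for the signal-to-background ratio, adverse-event rates or any regimen contrast

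*Combined protocol and SAP*

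**What the plan says.** Section 7.2 of the combined protocol and SAP states the aim: "we will use descriptive data on signal to background noise and safety data by tumor type to identify optimal dosing and timing of indocyanine green". It places an interim analysis "after approximately 185 subjects are treated at the 2.5mg dose and 185 at the 5mg/kg dose".

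Section 7.4 gives the method: "All data are summarized, with means and standard deviations for continuous variables and proportions for categorical variables". It adds graphs for exploration, says "Analyses will be primarily descriptive", and refers back to the preceding sections for the rest.

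The only interval in those sections is in 7.1, where the team will estimate sensitivity and specificity and "calculate Bayesian 90% probability intervals around them". It is not planned by dose, timing or tumour type.

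Section 7.3 says "There is no sample size calculation for this study" and describes the design: "we propose a 500 patient non-randomized prospective design". Section 1.6 allows infusion at any time up to 72 hours before surgery, or a 25 mg bolus at induction. It also says that the interim signal-to-background ratio will settle the best timing and steer later infusions in this and future protocols.

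The documents define no timing windows, list of tumour types, minimum cell size or selection rule.

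**The concern.** A standard deviation describes how much subjects vary. It does not show how well a regimen's mean is known. A mean and SD from 12 subjects look much like those from 185 unless an interval is attached. The data are to be viewed by tumour type, and timing is one of the things being optimised, so some comparisons may rest on few subjects. The apparent leader in such a comparison is partly selected for good luck.

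The ratio is positive, and multiplicative comparisons suit it. If it is also right-skewed, which the documents do not say, a few bright cases will pull the arithmetic mean.

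The result has consequences. It sets timing for the rest of this study, feeds later protocols and, under 7.3, informs a future randomised trial.

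**Working it through.** **No stated figure to reproduce.** Section 7.3 gives 500 subjects without a calculation, and no SD, effect size or power is stated.

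**1. Cell sizes (assumed, evenly filled).**
- Interim, dose only: about 185 + 185 = 370 subjects. Three tumour types give 370/(2 × 3) ≈ 62 per cell, and five give 370/(2 × 5) = 37.
- Whole study, dose by timing: Section 1.5 reports 327 consented, 4 still awaiting infusion and 296 infused. Scaling up, 296/323 × 500 ≈ 458, or about 460. Two doses in three assumed 24-hour bands plus the induction bolus make 7 groups. With five tumour types, 460/(7 × 5) ≈ 13 per cell.

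**2. Apparent advantage of the top regimen when all are equal.** Assume a log-normal ratio, so log-SD = √ln(1 + CV²). This gives 0.385, 0.555 and 0.833 at CV 40%, 60% and 100%. The expected maximum of k standard normal values is 0.564 for k = 2 and 1.352 for k = 7. The typical excess of the top geometric mean over the common true value is exp(E[max] × log-SD/√n) − 1.

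| Groups compared | n per cell | CV 40% | CV 60% | CV 100% |
|---|---|---|---|---|
| 2 | 62 | 2.8% | 4.1% | 6.1% |
| 2 | 37 | 3.6% | 5.3% | 8.0% |
| 7 | 13 | 15.5% | 23.1% | 36.6% |

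Uneven filling would make some cells smaller still.

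**3. What an interval would show.** The 95% half-width for a difference between two cell means is t × √(2/n) in SD units: 0.36 SD at n = 62 and 0.85 SD at n = 12. For adverse events, 0 of 62 is compatible with a rate up to 5.8%, and 0 of 12 with a rate up to 26.5% (exact).

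**4. The January 2019 adverse events with intervals added.** Denominators are in Section 1.5 (186 at 5 mg/kg, 110 at 2.5 mg/kg) and percentages in 1.7.1. The rebuilt category counts are 10 + 17 + 6 + 3 = 36 and 7 + 5 + 2 + 3 + 2 = 19, which match the stated totals. Differences are 5 minus 2.5 mg/kg in percentage points, with 95% Newcombe intervals.

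| Category | Counts | Difference | 95% interval |
|---|---|---|---|
| Vascular | 10 vs 7 | −1.0 | −7.6 to 4.4 |
| Arm pain or discomfort | 17 vs 5 | +4.6 | −2.0 to 10.2 |
| General | 6 vs 2 | +1.4 | −3.5 to 5.3 |
| Administration site | 3 vs 3 | −1.1 | −6.2 to 2.4 |
| Gastrointestinal | 0 vs 2 | −1.8 | −6.4 to 0.6 |

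For arm pain, the Wilson limits are 5.8-14.1% and 2.0-10.2%. The lower limit is 4.6 − √(3.3² + 5.7²) ≈ −2.0, and the upper is 4.6 + √(5.0² + 2.5²) ≈ 10.2.

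One caution: the counts sum to 55 events in 35 patients. These intervals treat each event in a category as a separate subject, so they are approximate, and too narrow if one subject contributes several.

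**The case against.** A reader might infer that the plan picks the regimen with the highest cell mean. It does not say so. Section 3.3 weighs signal against safety, the Study Summary and 3.1 leave dose and time to the PI or neurosurgeon, and 1.6 adds scheduling. The table in step 2 therefore shows how far chance can mislead, not what a stated rule would do.

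A reader might also take 16-37% as the expected error. That rests on a grid of five tumour types and three timing bands that is not in the documents. Section 1.6 says infusions began the day before surgery, so evenly filled bands are doubtful, and graphs need not cut timing into cells. With dose alone the figure is 3-8%, and with about 185 per dose pooled over tumour types chance selection is minor. The skew and the CVs are assumptions too. Moving to the log scale does not remove the selection effect, since step 2 is itself on that scale. The intervals are what make the effect visible.

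Nor do the documents show that adverse events will be seen only in tumour-type cells. Section 1.7.1 already pools them by dose, and the second paragraph of 7.2 lists safety without a split.

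Finally, descriptive analysis is normal in a feasibility study, Section 1.6 gives the interim ratio authority over timing and not over dose, and the interim comes after about 370 of 500 subjects. All of this stands and limits the size of the point. It does not supply an uncertainty measure for a comparison meant to guide later infusions.

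**Conclusion.** The point holds as a gap in the analysis plan. Optimal dose and timing are to be identified from summaries with no interval for the ratio, the adverse-event rates or any contrast between regimens. The possible overstatement runs from about 3-8% (two doses, 37-62 per cell) to 16-37% (seven groups, 13 per cell). Both ranges assume equal regimens, even filling, a log-normal ratio and a CV of 40-100%.

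Three stronger inferences are not supported. Intervals that include zero do not show the two doses to be equally safe. Intervals would not make the comparison causal: the PI chooses the regimen using tumour type, timing and the ratio itself, and dose changed during the study. The ratio is also not the only criterion named: Part IIb and Section 2 base the optimisation on sensitivity and specificity, while 1.6, 3.3 and 7.2 use the ratio. Those passages need reconciling, as does the interim trigger, which prints the lower dose in mg where 1.5 and 1.6 use mg/kg.

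**What to change.** Amend 7.2 and 7.4 as follows.

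1. Analyse the log signal-to-background ratio. Report geometric means and between-regimen ratios with 95% intervals, first overall with adjustment for tumour type, then by tumour type with cell sizes shown.
2. Report adverse-event rates by regimen, pooled over tumour types and counting subjects, with exact 95% intervals. This extends what 1.7.1 already does by dose; for example, 7 of 110 has an exact interval of 2.6% to 12.7%. Keep the tumour-type split as a listing.
3. State that the comparison is exploratory because regimens are not randomised, and name no optimum where the intervals do not separate the regimens.

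Partial pooling across tumour types can be an optional sensitivity analysis. With few types its variance component would be poorly estimated. A probability that each regimen is best should not be reported, because non-random choice of regimen would make it look more certain than it is.

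The cost is SAP wording and a simple adjusted model, with no new data and no change to any regimen. Tables become slightly less simple, and the statement of an optimum becomes more cautious.
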